Section D: Purpose and Objectives

This is an exploratory randomized controlled trial study to test feasibility, acceptability, and proof of concept efficacy of Continuous Diffusion of Oxygen (CDO) adjunct therapy for decreasing healing time and reducing tissue dehiscence post breast reconstruction. We will assess the benefit of this novel adjunct therapy on successful closure, tissue oxygenation, scar appearance, and patients centered outcomes including perception of benefit, pain, sleep quality, and quality of life. Since all procedures are bilateral, an internal randomization will be performed based on breast side (left or right). The patients will be given CDO in one breast defined as intervention breast. A 5x5 cm CDO dressing will be placed by the plastic surgeon over the T-inframammary fold after the Dermabond glue and Prineo tape are placed. Then, Silagen (a silicon sheet) will be placed on top of the CDO dressing to secure it in place. The remaining parts of the incision will be covered with Dermabond Glue and Prineo tape. On the contrary, the control breast will be given the standard dressing (Dermabond + Prineo tape). The study device OxyGeni is a Class II medical device which has US Food and Drug Administration (FDA) 510(k) clearance, CE-Mark approval and a Health Canada license for the treatment of wounds.

Outcomes will be assessed on weekly-basis up to 4 weeks. Here are the aims and hypotheses for this study:

Aim1: To assess effectiveness of CDO adjunct therapy in reducing the likelihood of wound complication post-surgical

closure.

H1: CDO adjunct therapy will reduce the likelihood of surgical wound complication including dehiscence and its volume, infection or surgical revision, compare to standard of care dressing.

Aim2: To assess changes in skin perfusion in patients treated with CDO adjunct therapy.

H2: CDO adjunct therapy will improve tissue oxygen saturation in >50% of the patients as compared to baseline (measurements at baseline, 2 weeks, and 4 weeks).

Aim3: To evaluate changes in quality of life, anxiety during dressing change, and psychosocial parameters in patients with a surgical wound treated by CDO adjunct therapy

H3: CDO adjunct therapy will improve subject quality of life, reduce anxiety, and reduce perceived pain and physiological stress response during dressing change compared to the control group.

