1) Baseline (Surgery Day, Week 0) 2) Visit 1 (Week 1 Post-Op) 3) Visit 2 (Week 2 Post-Op) 4) Visit 3 (Week 3 Post-Op) 5) Visit 4 (Week 4 Post-Op) 6) Visit 5 (minimum of 6 months Post-Op) *optional

Baseline: Subjects will be randomized to internal control. Since all procedures are bilateral, an internal randomization will be performed based on breast side (left or right). The patients will be given CDO in one breast defined as intervention breast. A 5x5 cm CDO dressing will be placed by the plastic surgeon over the T-inframammary fold after the Dermabond glue and Prineo tape are placed. Then, Silagen (a silicon sheet) will be placed on top of the CDO dressing to secure it in place. The remaining parts of the incision will be covered with Dermabond Glue and Prineo tape. On the contrary, the control breast will be given the standard dressing (Dermabond + Prineo tape).

Visits 1-4: All patients will have baseline assessment including visual, dermal, and tissue oxygen saturation level. The status of wound closure and presence of wound complication will be monitored every week. Each subjects will need up to 5 visits including baseline assessment, and weekly assessment up to 4 weeks or full wound healing or surgical revision, whichever comes first. At each visit, patients will be provided standard of care treatment including regular wound dressing change. Table 1 in attachments' section summarizes the key measurement at each study visit. At Visit 4, the CDO therapy will be removed. Subjects will then have the option to return at minimum 6 months later for a final follow-up visit listed below.

Visits 5: Optional follow-up visits. This visit can also be done remotely should the person not be available to attend the clinic.

Inclusion Criteria:

18-85 years of age. Ability to provide informed consent. Presence of a wound due to surgical intervention and closure. Subject or responsible caregiver is willing and able to maintain the required Continuous Diffusion of Oxygen (CDO) system (if assigned to the intervention group) and applicable dressing changes

Exclusion Criteria:

Active Drug/alcohol abuse (or history of drug/alcohol abuse in last 1 month); excessive lymphedema; presence of active infection; subject has a history of or any intercurrent illnesses or conditions that would compromise the safety of the subject according to judgement of a qualified wound specialist.

F2. Procedure

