Please note that subjects will be consented before performing any study related measurements. This study will not bring any direct costs to the subject. The subject's medical insurance will be billed for all standard of care procedures.

Eligible subjects will be internally randomized and will receive the intervention for 4 weeks. Each subjects will receive standard of care for wound treatment. Intervention side will receive adjunct Continuous Diffusion of Oxygen (CDO) therapy using a novel dressing, which facilitates continuous supply of oxygen to the wound inside the wound dressing using a portable device named OxyGeni . We will collect patient demographics (e.g., age, sex, height, weight, race, ethnicity, marital status, level of education, etc), relevant medical history (e.g., comorbidity, type of surgery, number of prescription and over counter medication, etc), and relevant social factors (e.g., marital status, years of education, type of work, tobacco history, etc) at baseline. Primary outcomes include tissue oxygenation (assessed using Kent Imaging system) and incidence of wound complications (e.g. dehiscence, infection, and surgical revision). Primary outcomes will be assessed at baseline and on a weekly basis for up to 4 weeks. Secondary and exploratory outcomes include inflammation (assessed using a KENT camera), pain (assessed visual analog scale). The secondary and exploratory outcomes will be assessed at baseline and week-4. Other optional assessments include quality of life (NIH Global Health PROMIS), depression (Center for Epidemiologic Studies Depression Scale, CES-D), cognitive function MoCA), and psychosocial metrics (e.g. fatigue, anxiety, frailty, sleep, etc). These assessments are optional and will be done upon time availability and patient acceptance. We anticipate that duration of all assessments will not exceed 60 minutes. We will be reviewing the billing records for our

patients to explore costs of both groups. We may visit the patient's home for an appointment that doesn't require the physician present or to fix any issues with the device.

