The plastic surgeon ([name]) will perform the initial consultation with the patient in the clinical setting (initial and pre-operative consult). Once the patient is aware of the study protocol, the study coordinator will obtain consent on the day of surgery. Research coordinators are responsible to revise the medical records (e.g., Epic) on a weekly basis in order to screen possible candidates undergoing reduction mammoplasty that could fit for the study. If the patient fits the criteria, the research coordinator will communicate the candidate's information (e.g., name, date of surgery) to [name]. Candidates will be consented on the day of surgery upon plastic surgeon approval.

Baseline visit: After consenting the patient, the research coordinator will attend to the surgery. When the plastic surgeon closes the incision, the research coordinator will obtain the tissue oxygenation image using (non-invasive) NIRS, and then the surgeon will place the dressing immediately (The CDO dressing will be applied on the T-inframammary fold of the breast incision), followed by Silagen directly on top. After surgery, the research coordinator will wait until the patient is coherent in the post-operative recovery area. Then, they will educate the patient on proper device use.

After the surgery, the study will include 4 weekly follow-up visits, with visits in between for additional dressing changes asneeded. The 4 weekly follow-up visits are described below.

Visit 1, 1 Week Post-Op *duration: 50 minutes. Research staff will perform tasks as described above: Pain Questionnaire, NIRS Imaging, Digital Photograph, Adverse Event Reporting, Wound Assessment, Dressing Change and Device Education. Plastic surgeon will remove the CDO dressing in his normal post-operative clinic appointment, and the female research coordinator will obtain the near-infrared spectroscopy image, digital image, and wound assessment. After that, the research coordinator will cover the incision with a new CDO dressing. All measurements and procedures will be performed by a female research coordinator under ethics protocols.

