The primary outcomes of this study are 1) tissue oxygen saturation level measured using Kent Imaging system and 2) incident of wound related adverse events (e.g., incident wound dehiscence, infection, scar size, and surgical revision). Secondarily outcomes include pain, wound outcomes (e.g. wound size, scar size, wound healing rate, etc assessed using digital photography), area of inflammation (assessed using KENT), and pain (assessed using VAS). Exploratory outcomes include patient quality of life, sleep quality, anxiety, and depression. Baseline between group comparison will be dine using two-sample t-tests, Mann-Whitney U-test, or Chi-square depend on scale/distribution of the variables (i.e., parametric, non-parametric, or binary). We will use general mixed linear model and post-hoc analysis to examine difference between

groups (time, group, and time X group effect) for skin perfusion. We will adjust the results based on baseline incision wound size and duration between baseline and last visit assessment. Subjects with at least one week continue treatment will be included in the analysis. Controlled variables include age, BMI, baseline vascular health. We will use chi-square to estimate whether the number of wound complication incidents is less in the intervention group compared to the control group. Chi-square or repeated ANOVA or Mann-U test depend on scale/distribution of the variable will be used for secondary and exploratory outcomes.

Section H: Potential Risks/Discomforts

H1. Potential Risks/Discomforts

Describe and assess any potential risks/discomforts; (physical, psychological, social, legal, or other) and assess the likelihood and seriousness of such risks:

As any new investigational device, there are some risks, which are anticipated to be minimal in this study. Some of potential risks could be: * Skin related discomfort, erythema (redness), skin rash, dryness and itching. * Skin allergic reaction to dressing adhesive. * Tenderness/minor ache around the dressing application area * Heat sensation and/or perspiration with wearing dressing * Some impairment of mobility due to dressing unit

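### The one-week treatment rule selects the oxygenation analysis set after randomisation with no all-randomised analysis, and the stop-at-healing clause conflicts with the fixed week-4 assessments

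*Combined protocol and SAP*

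**What the plan says.** **Analysis set.** F1 randomises breast side at baseline, the day of surgery. G2 names tissue oxygen saturation and wound-related adverse events as the primary outcomes. It plans a mixed linear model for differences between "groups (time, group, and time X group effect) for skin perfusion", adjusts for incision size at baseline and for the time from baseline to the last assessment, and then says "Subjects with at least one week continue treatment will be included in the analysis". Complications come two sentences later: "We will use chi-square to estimate whether the number of wound complication incidents is less in the intervention group compared to the control group". That sentence names no analysis set. The document contains no all-randomised set, no sensitivity analysis and no rule for missing data.

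**Schedule.** F1 prescribes "weekly assessment up to 4 weeks or full wound healing or surgical revision, whichever comes first". The same section says "At Visit 4, the CDO therapy will be removed". F2 says "Eligible subjects will be internally randomized and will receive the intervention for 4 weeks" and "After the surgery, the study will include 4 weekly follow-up visits". F2 also places secondary and exploratory outcomes at baseline and week 4, and describes Visit 4 with no condition on healing. H2 in Section D expects CDO to "improve tissue oxygen saturation in >50% of the patients as compared to baseline (measurements at baseline, 2 weeks, and 4 weeks". Section C says the closure tape stays on for three weeks, that incisions are usually healed when it comes off, and that dehiscence, if any, usually appears in the second to third week.

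**The concern.** Randomising the side within each patient protects the CDO-versus-control contrast only while the analysed patients are chosen independently of what happens afterwards. A minimum of one week on treatment is known only after randomisation. The device is worn on one side only, so the reasons to stop early (skin reaction, allergy to the adhesive, burden of the unit, all listed in H1) plausibly lie on the CDO side. If they are related to that side's oxygenation, the retained pairs give a biased contrast, and the plan has no second analysis that would reveal it.

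The stopping clause raises a separate problem. If assessment ends when the wound has healed, the week-4 oxygenation values come mainly from slow healers. Week 4 is one of H2's named time points.

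**Working it through.** The plan states no effect size, SD, power or dropout rate, and G1 bases N = 30 on budget and feasibility. There is no figure to reproduce, so what follows shows possible sizes under stated assumptions.

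**1. Bias in the oxygenation contrast.** Assume 30 pairs, no true effect, correlation ρ between a patient's two breasts, and a pair dropped whenever the CDO-side value is in the lowest share q. With φ the normal density and z_q the q-quantile, the bias in SD units is (1 − ρ)·φ(z_q)/(1 − q). For ρ = 0.5 and q = 0.10 this gives 0.097. Simulation (40,000 runs, paired t-test, two-sided 5%, ρ = 0.3 to 0.7) gave:

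| q (assumed) | Pairs kept | Bias towards CDO, SD | Type I error |
|---|---|---|---|
| 5% | 28.5 | 0.03–0.07 | about 6% |
| 10% | 27 | 0.06–0.14 | 7%–9% |
| 20% | 24 | 0.10–0.25 | 10%–18% |

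With all 30 pairs, type I error was 4.9% to 5.1%. With exclusion unrelated to outcome, the bias was zero to within simulation error. Exclusion that depends wholly on the CDO-side value is a severe assumption, so a looser link would give less bias.

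**2. Complications, only if the rule covers them.** Let p be the complication risk per breast (Section C: 10%–15%, assumed to apply per breast), f the share of CDO-side complications that end CDO before one week (assumed 0.1), and P11 the chance that both breasts have one. With no true effect, the risk ratio in the retained set is (1 − f)/(1 − f·P11/p).

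- p = 0.10, P11 = 0.0100 (independent breasts): 0.9/0.99 = 0.91.
- p = 0.15, P11 = 0.0913 (latent correlation 0.8): 0.9/0.939 = 0.96.
- Expected exclusions, 30·p·f: 0.30 to 0.45 of a patient.

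Section C puts dehiscence in weeks 2–3, after the one-week mark, so f is probably small.

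**3. H2's threshold, illustration only.** 15/30 = 50.0% does not exceed 50%. Without one non-improver it becomes 15/29 = 51.7%, and without two, 15/28 = 53.6%. Starting from 14/30 = 46.7% it takes three: 14/27 = 51.9%. The result must lie near the threshold: the chance of exactly 15 of 30 is 14%, 8% or 1% if the true share is 50%, 60% or 70%.

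**4. Schedule.** Compatible with stopping at healing: the wording in Section D, F1 and F2 that gives four weeks and five visits as maxima. Not compatible: H2's week-4 measurement, four weeks of intervention (F2), secondary outcomes at week 4 (F2), CDO removal at Visit 4 (F1) and the unconditional Visit 4 (F2). F1 also does not say whether one or both breasts must heal before assessment ends.

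**5. What the clause could cost.** If a share h is healed by week 3 and then leaves, 30(1 − h) pairs remain at week 4: 15 for h = 50%, 9 for 70%, 3 for 90% (h assumed). If m patients lack week 4 and x of the rest improved, the share among all 30 lies between x/30 and (x + m)/30. For m = 6 and x = 14, the observed 14/24 = 58% is compatible with 14/30 = 47% to 20/30 = 67%.

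The mixed model loses less, because weeks 1–3 remain. With exchangeable correlation r of the between-breast difference over weeks, R² = 3r²/(1 + 2r), and the SE ratio is √(30·[(1 − R²)/(30 − m) + R²/30]). At m = 6 and r = 0.3, 0.5, 0.7 this is 1.10, 1.075 and 1.05, against √(30/24) = 1.12 from week 4 alone. This holds only if the values are missing at random given the model.

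**The case against.** This is an exploratory pilot, and a minimum-exposure set is a natural choice for asking whether oxygen delivered to the wound raises tissue oxygenation. Both breasts of an excluded patient leave together, so the sides stay balanced. These points stand, and they are reasons to keep the one-week set as a sensitivity analysis. They do not remove the bias when stopping depends on the CDO side, and G1 allows the initial results to support a larger sample.

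A reader might infer that only the CDO device can trigger exclusion. G2 does not define treatment, and F1 and F2 also use the word for standard care, so this is plausible but not stated. A reader might also infer from H1's remark on daily charging that poor chargers are the ones removed. No passage links charging to the one-week rule.

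On the schedule, the maxima in Section D, F1 and F2 allow the listed visits to be read as an upper limit. F1 also refers to an attached table of measurements by visit, which is not in the available text and might settle the matter. That softens the conflict but leaves the fixed week-4 statements unexplained. G2's adjustment for time to last visit does not help: healing or revision sets that time after randomisation, and both breasts share it.

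**Conclusion.** Both parts hold and should be fixed, with limits on their size. The oxygenation analysis is restricted by a post-randomisation condition and has no all-randomised counterpart. The bias is unknown, may be small, and is zero if stopping is unrelated to outcome. The figures in the first table rest on assumed q and ρ and a severe exclusion rule.

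The stopping clause is in tension with several fixed week-4 statements. Since Section C expects healing at about three weeks, following it literally could remove many week-4 values according to healing, in an unknown direction and number.

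Three stronger readings are not supported:

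- **The rule distorts the complication result.** Its scope there is not stated, and fewer than half a patient would be excluded under the assumption used.
- **One exclusion would decide H2.** G2 plans no responder analysis, H2 is a change from baseline rather than a left–right contrast, and the example needs a result near 50%.
- **The week-4 acceptability questionnaire misses early device stoppers.** No passage ends follow-up when the device is stopped.

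**What to change.** **(a) G2, analysis set.** Make the primary analysis of each outcome all randomised patients, each breast as assigned and as paired data, whatever the duration of CDO. Fit the mixed model by likelihood to all available visits. Keep patients with at least one week of CDO as a sensitivity analysis, and say which outcomes it covers. Report how many randomised patients have no post-baseline data, and how many stopped CDO before one week and why.

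**(b) Schedule.** Reconcile F1's stopping clause with H2 and F2 so that outcome assessment of both breasts continues at the scheduled visits to week 4, with dates of healing and revision recorded. This concerns assessment only and proposes no treatment rule.

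**(c) H2.** If its share at week 4 is reported, give the number missing by healing status, with best-case and worst-case bounds.

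**Cost.** New wording in G2 and consistent wording in Section D, F1 and F2, plus already scheduled visits that would otherwise be skipped. Early stoppers may dilute the estimate: if k of 30 have no gain (assumed), the overall mean gain is (30 − k)/30 of that in the one-week set, i.e. 97%, 93% or 90% for k = 1, 2 or 3. The sensitivity analysis will show this.

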There will be an optional follow up visit up to three and six months after the last visit to determine any potential wound complications (e.g., patient unhappiness with the appearance of scar, infection and quality of life etc). During this visit, study coordinator will photograph both incision sites using near-infrared spectroscopy (NIRS, KENT camera) and a digital photo. Practitioner will assess scarring using the SCAR and/or POSAS scale.

Dressing Change: All patients will have their dressing changed weekly (screening/initial visit and visits 1-4), the intervention site will be treated continuously with oxygen from the OxyGeni device. Prior to application of the OxyGeni, research staff will: Select a 5x5cm OxySpur O2 dressing that will cover the wound; Wrap dressing as directed by physician. This may facilitate delivery of oxygen to the incision site or wound bed.

Data collection: - Medical History: Relevant patient medical history (e.g. type of cancer, type of therapy, other comorbidity such as diabetes and stroke, history of surgery, number of prescription and over counter medication, etc) will be collected at baseline via questionnaire or patient electronic health record.

- Social Factors: marital status, years of education, type of work, tobacco history (pack years, current smoker, current use of chewing tobacco, previous smoker, no tobacco history), drug history (current, previous history, no drug history), and alcohol history. These factors will be collected at screening/baseline visit.

Tissue Oxygen Saturation (primary outcome): Tissue oxygenation level will be assessed using Kent Imaging system at baseline and every study visit. The device uses light in the near-infrared spectrum that harmlessly passes through the skin and reflects off the blood supplying the tissue to determine tissue oxygen saturation, a key indicator of tissue health. The NIRS light has two key features that make it useful for measuring the viability of living tissue. Firstly, NIRS light is not absorbed by tissue as much as visible or ultraviolet light. Secondly, NIRS light is mainly absorbed by hemoglobin and water. Most importantly, the wavelength dependent light absorption of hemoglobin differs if it is carrying oxygen from when it is not. This makes NIRS light very useful in detecting oxygenated and deoxygenated blood, which conveys a comprehensive picture of tissue health and the healing capacity of wounds or tissue transplants.

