Visit 5, at minimum 6 months post-op *duration: 50 minutes. This is an optional visit where research staff will take a NIRS image, a Digital Photograph, report adverse events since last visit, and assess patient scar satisfaction using validated questionnaires (PASS and POSAS). Moreover, the plastic surgeon will provide their observation of the scarring using validated questionnaires (SCAR and POSAS). The patient will be seen in the Vascular Clinic (Procedure Room). Female research coordinator will perform all measurements and questionnaires under ethics protocol. Should the patient not be available to attend the clinic in-person, they will have the option to do the questionnaires remotely and upload digital photos of the area via RedCAP. This study visit is added to provide long-term information regarding scarring and effect of study device on long-term healing outcomes.

The research coordinator will make sure at all times that patient does not experience discomfort and all ethical protocols will be followed.

Section G: Sample Size/Data Analysis

G1. Sample Size

How many subjects (or specimens, or charts) will be used in this study? Local: 30 Worldwide: 30

Please indicate why you chose the sample size proposed:

This is an exploratory proof of concept study. The anticipated sample size (n=30) is selected based on resource/budget availability and feasibility to be completed within one year. This sample size is estimated to be sufficient to determine feasibility and proof of concept efficacy of Continuous Diffusion of Oxygen (CDO) adjunct therapy to improve tissue oxygen supply and reduce likelihood of adverse events. Upon initial results and availability of budget, the sample size may be increased to clinically validate the initial observation. In this case, an addendum will be submitted to increase sample size if needed.

G2. Data Analysis

Provide a description of your plan for data analysis. State the types of comparisons you plan (e.g. comparison of means, comparison of proportions, regressions, analysis of variance). Which is the PRIMARY comparison/analysis? How will the analyses proposed relate to the primary purposes of your study?

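### The StO2 mixed model does not name each breast's pre-dressing StO2 as a covariate, so the within-patient contrast may be less precise than the data allow

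*Combined protocol and SAP*

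**What the plan says.** Sections D and F1 randomise side within each patient: one breast receives CDO and the other the standard dressing. Section G2 states "The primary outcomes of this study are 1) tissue oxygen saturation level measured using Kent Imaging system" and gives the model in one sentence: "We will use general mixed linear model and post-hoc analysis to examine difference between" "groups (time, group, and time X group effect) for skin perfusion". Aim 2 in Section D pairs skin perfusion with tissue oxygen saturation, so I read this as the StO2 model.

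Two covariate sentences follow. The first is "We will adjust the results based on baseline incision wound size and duration between baseline and last visit assessment". The second is "Controlled variables include age, BMI, baseline vascular health". Neither names baseline StO2.

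On data collection, Section F2 says "Tissue oxygenation level will be assessed using Kent Imaging system at baseline and every study visit". Its description of the baseline visit puts the first image after closure and before the dressing goes on, so it is a true pre-treatment value. H2 in Section D is framed against baseline.

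G2 does not state the random effects, whether baseline is a level of time, or what baseline vascular health means.

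**The concern.** The covariates chosen are mostly ones that cannot help a left-right comparison, and the one most likely to help is not listed. Age and BMI are identical for the two breasts of a patient. What can vary between breasts, and may persist from surgery into follow-up, is local perfusion, and the baseline image measures exactly that.

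The sample size gives no slack: "The anticipated sample size (n=30) is selected based on resource/budget availability and feasibility to be completed within one year". With 30 patients fixed by budget, the efficiency of the analysis is one of the few things the plan can still improve. Section G1 also says that initial results may lead to a larger sample, so an imprecise StO2 estimate would carry into that decision.

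**Working it through.** **Inputs.** From the documents: 30 patients, two breasts each, StO2 at baseline and weeks 1-4, side randomised. Not in the documents, hence assumed: all standard deviations and ρ, the correlation between a patient's CDO-minus-control difference at baseline and at follow-up. The plan gives no power or precision figure for StO2, so there is none to reproduce.

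**Step 1: patient-level covariates.** Let a covariate X take value Xᵢ for patient i with coefficient β. In the side difference it contributes βXᵢ − βXᵢ = 0. A simulation (150 replicates; breast SD 2, residual SD 4; ρ = 0.32) agrees. With a patient random intercept and balanced data, adding age, BMI and a patient-level vascular score changed the treatment estimate by less than 1e-14 and left its mean SE at 0.734. Without a patient effect, the covariates lowered the model SE from 1.737 to 1.631, but that model ignores the pairing. The redundancy therefore depends on a patient effect, which G2 does not state.

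**Step 2: how baseline enters.** Let σ² be the variance of the side difference at one time, assumed equal at baseline and follow-up.

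- Follow-up only: σ²/n
- Change from baseline (baseline a freely estimated time level): 2(1−ρ)σ²/n
- Adjusted for baseline: (1−ρ²)σ²/n
- Change over adjusted: 2(1−ρ)/(1−ρ²) = 2/(1+ρ)
- SE saving against follow-up only: 1 − √(1−ρ²)
- Follow-up-only sample size with the same precision as 30 adjusted patients: 30/(1−ρ²)

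| ρ (assumed) | Change, relative variance | Adjusted, relative variance | Change / adjusted | SE saving vs follow-up only | Equivalent n |
|---|---|---|---|---|---|
| 0 | 2.00 | 1.00 | 2.00 | 0% | 30 |
| 0.3 | 1.40 | 0.91 | 1.54 | 4.6% | 33 |
| 0.5 | 1.00 | 0.75 | 1.33 | 13.4% | 40 |
| 0.7 | 0.60 | 0.51 | 1.18 | 28.6% | 59 |

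**Step 3: the mean of weeks 1-4.** A four-visit mean is less noisy than one baseline reading, so equal variance no longer holds. Assume breast SD 3 and residual SD 3. For the side difference:

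- baseline variance 2(9 + 9) = 36
- follow-up mean variance 2(9 + 9/4) = 22.5
- covariance 2 × 9 = 18, so ρ = 18/√(36 × 22.5) = 0.63
- follow-up only: SE √(22.5/30) = 0.87
- change: 36 + 22.5 − 2 × 18 = 22.5, SE 0.87
- adjusted: 22.5 − 18²/36 = 13.5, SE √(13.5/30) = 0.67

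Both unadjusted routes have 22.5/13.5 = 1.67 times the adjusted variance. For a four-week mean, 2/(1+ρ) thus understates the cost of the change contrast.

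**Step 4: the group main effect.** If baseline is one of five time levels and the equally weighted group effect is taken as the estimate, a constant effect δ in weeks 1-4 is estimated as (0 + 4δ)/5 = 0.8δ, a 20% dilution.

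**Step 5: the downside.** In the simulation at ρ = 0, adjustment moved the empirical SD of the estimate from 0.528 to 0.537, a slight loss.

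**The case against.** The strongest reply is that baseline is not omitted. StO2 is measured at baseline, the model has time and time X group, and H2 is relative to baseline, so baseline is naturally the first time level. That is a fair reading, and the documents do not support saying that the plan ignores baseline. It does not remove the loss: with baseline means left free, the interaction contrast is a change from baseline and carries the 2/(1+ρ) penalty.

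Other stronger readings should be resisted.

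- **That the listed covariates do damage.** With a patient effect they leave estimate and SE as they were.
- **That the list is wholly patient-level.** Incision size can differ between breasts, and vascular health is undefined.
- **That vascular health is never measured, so patients would be lost.** Section F1 refers to a Table 1 of measurements that is not in the text available here, and Section P lists devices that the visit text does not describe.
- **That the effect will be diluted by 20%.** G2 also plans the interaction and post-hoc comparisons and does not make the averaged group effect the estimate.
- **That the result will be biased.** Side is randomised.

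It is also true that ρ is unknown. Baseline is imaged at closure, and side differences then may predict weeks 1-4 poorly; near ρ = 0 there is no gain over a follow-up-only analysis. Finally, H2 concerns the share of patients who improve from baseline. Neither G2's mixed model nor the proposed one estimates that share, so it needs its own summary.

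**Conclusion.** The point holds as one of precision and specification in a pilot. G2 does not name each breast's pre-dressing StO2 as a covariate and leaves open how baseline and the pairing enter the model. Under equal variances, the cost relative to baseline adjustment is a variance ratio of 1.54 to 1.18 for a change contrast over ρ of 0.3 to 0.7. Relative to follow-up only, the forgone SE reduction runs from nil at ρ = 0 to 28.6% at ρ = 0.7. At ρ = 0.5, adjustment gives 30 patients the precision of 40 analysed on follow-up alone.

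All these sizes rest on assumed values of ρ, and those in Step 3 on assumed SDs as well. Exact cancellation of age and BMI needs a patient effect and balanced data; with missing visits it is only approximate.

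**What to change.** In G2, specify the StO2 model as follows.

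- Response: StO2 at weeks 1-4.
- Fixed effects: breast (CDO or control), week, and breast X week.
- Random effects: patient, and breast within patient.
- Covariates: each breast's baseline StO2 together with the patient's mean baseline StO2, so that the within-patient slope is not mixed with the between-patient slope. Keep baseline incision size.
- Main StO2 estimate: the CDO-minus-control difference over weeks 1-4, with its confidence interval.

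Keeping baseline as a response, with the two breasts' baseline means constrained equal, serves the same purpose. Age and BMI may stay or be used for description only. Define baseline vascular health, or drop it from the model.

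The cost is wording in G2 and one check: F2 does not say outright that both breasts are imaged at baseline, and the sponsor should confirm it. If they are, no new data are needed. The statistical downside is at most a slight loss of precision if ρ is near 0.
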